8.1 Data Analysis

Data analysis will be performed using the appropriate statistical analysis software, such as IBM SPSS, SAS, etc. Descriptive statistics will be used to discuss demographics of the participants. An alpha level of 0.05 will be used to determine statistical significance for all analyses.

Outcome variable:

- Feeding tube migration (yes/no).
 - Number of hours from insertion to tube movement
 - Forward migration/backward migration
 - Zone of the FT distal tip (figure 1)

Figure 1. FT Placement/Migration Zones

Independent variables: These variables that possibly have an association with FT migration will be collected and will help to inform the design of a larger R01 study.

- Patient bedside observation
 - Date/time of data collection
 - Date/time of feeding tube insertion
 - Documentation of dual verification at initial insertion

DrIFT 2 STUDY: DISPLACEMENT IN FEEDING TUBES

- Length of feeding tube
 - Diameter of feeding tube 10 FR, 8 FR, other
 - Rate of formula ____ ml/hr
 - Bolus via FT yes/no, volume ____ ml/hr, frequency: every ____ hours
 - Cortrak device serial number
 - Length of FT inserted ____ cm
 - Mark present on abdomen for receiver unit placement? If not, apply mark using surgical marker and indicated date/time.
 - bridle present (yes/no)
 - Patient position supine/HOB elevated 30 degrees (yes/no). If no, identify position.
- EMR
 - Medical record number on enrollment form that is linked to unique study number. Do not write MRN on data collection form.
 - Was dual verification performed (yes/no).
 - Was x-ray obtained for verification (yes/no)
 - CM mark at nares at time of original insertion
 - Patient demographics
 - Sex
 - Age
 - Weight
 - Diagnosis
 - Height in cm
 - Factors that may impact motility: abdominal compartment syndrome, gastric ileus, abdominal distension, ascites or hepatic enlargement
 - Metoclopramide (yes/no)
 - Erythromycin (yes/no)
 - Vasopressors: identify by name.
 - Vomiting/retching (yes/no)
 - Excessive coughing (yes/no) ask nurse
 - Observed pulling on FT (yes/no)
 - Ambulation (yes/no)
 - Sitting on side of bed or up in chair (yes/no)
 - Prone position
 - Transfer off unit for diagnostic test/surgery or procedure (yes/no) name of test_____ date/time_____
 - Endotracheal tube removed (yes/no) date/time_____
 - Endotracheal tube replaced (yes/no) date/time_____

9. Informed Consent Process

The primary risk for this study is microbial contamination with insertion of the stylet [12] – to mitigate this risk, the stylet will be cleaned with alcohol before every insertion. This study presents low risk level to the patients and a waiver of written informed consent is being requested.

10. Privacy and Confidentiality

Each participant will be assigned a unique study number, which will be known only to the site specific Sub-I and PI. This study number will be used to identify all data collected for the purpose of research. Data collection will be performed on printed forms by the PI or Sub-I. Data collection forms will contain only the participant's unique study number and will be de-

DrIFT 2 STUDY: DISPLACEMENT IN FEEDING TUBES

identified. Data collection forms will be stored temporarily during the data collection period in a locked office of the Sub-I. Data will then be entered into a spreadsheet on a password protected Parkview computer. Data will be maintained for a minimum of five years after the completion of the study. Only the investigators will have access to the study data.

Cortrak insertion tracings will be scanned for electronic storage. De-identified insertion tracings from each site, labeled with the file name containing unique study numbers only, will be sent to the other study site for confirmation of FT placement. Having two Sub-Is identify FT placement will increase fidelity of the study. If both Sub-Is are not in agreement regarding the zone of the distal FT tip, the other investigators on the study team (PI and Sub-I) will assess and come to consensus. Transmission of scanned insertion tracings will be sent by institutional email using the confidential setting.

An electronic file linking patient identifiers (human subjects' name, MRN, and study site) and unique study number will be kept in a file on the password protected computer of the PI. Only the principal investigator will have access to this file. The participant identification number will be kept separate from the data collected.

11. Risk/Benefit

11.1 Risk to Participants:

There are minimal risks associated with this study. Insertion of the FT guidewire and verification of FT placement using Cortrak is a standard procedure that can be performed any time that the clinician is uncertain about the position of a FT. The risk to the patient are primarily during the initial insertion, this study will only enroll patients who have the feeding tube currently in place.

The primary risk for this study is microbial contamination with insertion of the stylet [12] – to mitigate this risk, the stylet will be cleaned with alcohol before every insertion.

Loss of confidentiality is always a risk, participation in the study will remain confidential. All demographics and data collected for research purposes will remain confidential. Only the assigned unique study number will be used. Measures will be in place to mitigate the risk for loss of confidentiality, data will be stored on a password protected Parkview computer. Any paper data collection forms will be kept in a locked drawer in a locked investigators office.

11.2 Benefits to Participants:

There may not be any direct benefits to individual participants in this study. There may be benefits for future patients with small bore feeding tubes since findings from this study have the potential to influence frequency of feeding tube verification. Knowledge obtained from this study may be beneficial not only for the study sites, but internationally.

12. Safety Monitoring, Interim Analysis, and Stopping Rules

Our study contains no more than minimal risk to the participants.

13. Conflict of Interest

There is no conflict of interest with any of the researchers involved with this study.

14. Publication and Presentation Plans

DrIFT 2 STUDY: DISPLACEMENT IN FEEDING TUBES

Findings from this study will be presented by poster or podium at a national meeting, such as the National Teaching Institute (NTI) of the American Association of Critical-Care Nurses (AACN). Findings will also be disseminated in a publication, such as American Journal of Critical Care. Also, as per OH policy, we will plan to present the findings from this study at a Center for Nursing Research meeting.

15. References

1. Metheny, N.A., B.J. Stewart, and S.A. McClave, *Relationship between feeding tube site and respiratory outcomes*. JPEN J Parenter Enteral Nutr, 2011. **35**(3): p. 346-55.
2. Metheny, N., *Initial and Ongoing Verification of Feeding Tube Placement in Adults*. Critical Care Nurse, 2016. **36**(2): p. e8-e13.
3. Bourgault, A.M., et al., *Methods used by critical care nurses to verify feeding tube placement in clinical practice*. Critical Care Nurse, 2015. **35**(1): p. e1-e7.
4. Metheny, N.A., B.J. Stewart, and A.C. Mills, *Blind insertion of feeding tubes in intensive care units: a national survey*. Am J Crit Care, 2012. **21**(5): p. 352-60.

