The proposed study will use an electromagnetic placement device (EMPD), Cortrak* 2 Enteral Access System (EAS™), Avanos Medical, to verify FT position on a daily basis to assess for migration. The EMPD provides real-time FT placement data. A sensor located on the distal end of the FT guidewire communicates with a receiver unit which sits on the patient's abdomen. Three visual insertion tracings with varying views (anterior, lateral, and depth/cross-section) can be saved and printed for comparison. (See Figure 1)

Two previous studies have been completed with similar methodology. A pilot study of 50 subjects was performed using the original Cortrak* (2 insertion views) and found only minimal forward migration [9]. No reverse migration was reported in the Powers study.

DrIFT 2 STUDY: DISPLACEMENT IN FEEDING TUBES

A pilot study of 20 patients with 62 feeding tube assessment identified 8 migration events (5 retrograde and 3 forward), these events only occurred within the small bowel [10]. Based on this data, a recommendation could be made that there is no need to check feeding tube placement routinely q4hours. However, due to the small sample size, additional research is needed to confirm this finding. It is also unknown if there may be more migration with positioning changes, for example, up in the chair or prone position.

The proposed study will use an electromagnetic placement device (EMPD), Cortrak* 2 Enteral Access System (EAST™), Avanos Medical, to verify FT position on a daily basis to assess for migration. The proposed study will take place in critical care units at Parkview Health. The primary aim will be to determine if replication of the pilot study results in similar findings. We will also explore other factors that may be associated with FT migration, such as patient mobility (ambulation or sitting at bedside or prone position) and transporting out of the critical care unit for diagnostic procedures. We anticipate that results from this study will provide a better understanding of FT position and migration over time and ultimately influence recommendations for practice for frequency of routine FT verification. Standard of care for assessing feeding tube placement location every 4 hours will remain in place. The study will add an additional assessment for feeding tube location daily. This study will expand on the findings from the initial pilot study with a larger sample size.

3 Primary Objective

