4.1 Inclusion Criteria

- Adult ≥ 18 years old
- Critical care patients with small bore feeding tube inserted within last 24-48 hours
- Initial Cortrak insertion tracings: all 3 views available
- Cortrak guidewire available (these are typically saved in a plastic bag in the patient room following FT insertion).

DrIFT 2 STUDY: DISPLACEMENT IN FEEDING TUBES

Ethic/racial diversity, age, or sex are not anticipated to play a role, so our recruitment will not focus on a diverse sample.

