The sample size of 120 participants for this study was selected based on feasibility and consultation with a biostatistician. A sample size of 120 will detect feeding tube migration over time (effect size 0.18, 80% power, alpha 0.05) using mixed effects model. The effect size was calculated by a statistician based on preliminary data from our original pilot study.

Bivariate descriptive characteristics of the study population will be compared according to feeding tube migration status (yes/no). Differences in patient's clinical and demographic characteristics between the groups will be assessed by chi-square statistics for categorical variables and two-sample t-tests (or Wilcoxon for nonparametric) for continuous variables.

Time to feeding tube migration will be assessed via the Kaplan-Meier (KM) method for repeated events in 24-hour blocks [11]. Patients who experience feeding tube migration may also have additional forward/backward migration in subsequent 24-hour periods. Thus, the nonparametric estimate of the survival function has to accommodate the potential for repeated events. The likelihood of feeding tube migration according to time will be obtained by the KM estimator (no migration) and cumulative distribution function (migration), respectively. Other analyses may be performed if necessary.

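### Starting tip zone is available from the required insertion tracing but has no role as stratum or covariate, so the pooled migration rate is a weak basis for judging replication or advising on gastric tubes

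*Combined protocol and SAP*

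**What the plan says.** - **Aim.** The background states: "The primary aim will be to determine if replication of the pilot study results in similar findings". Section 3 words the primary objective as whether tubes migrate over time.
- **Pilot result.** "A pilot study of 20 patients with 62 feeding tube assessment identified 8 migration events (5 retrograde and 3 forward"; of these the background adds that "these events only occurred within the small bowel". It gives no number of assessments by tip zone.
- **Eligibility.** Section 4.1 admits "Critical care patients with small bore feeding tube inserted within last 24-48 hours" and requires "Initial Cortrak insertion tracings: all 3 views available". Sections 4.1 and 4.2 set no starting zone, quota or stratum.
- **Measurement.** Section 6.4 obtains the tracings from the original insertion and repeats them at follow-up. Section 10 has two readers identify tip zone, with consensus if they disagree.
- **Variables.** Section 8.1 places "Zone of the FT distal tip (figure 1" under the outcome, beside direction of migration and hours to movement. The independent variables do not include zone at insertion or at the start of an interval. The nearest items are length inserted and the centimetre mark at the nares.
- **Analysis.** Section 8 plans a Kaplan-Meier analysis for repeated events in 24-hour blocks, with no strata, and a comparison of patients' clinical and demographic characteristics by migration yes/no. A mixed effects model is named only in the sample-size statement (sections 6.1 and 8), without covariates. Section 8 also leaves room for further analyses, unspecified.

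**The concern.** The pilot finding that the background builds on is about location as well as frequency: every event was in the small bowel. A pooled rate is a weighted average of the zone-specific rates, and here the weights are whatever local placement practice supplies. Two studies with the same tube behaviour can differ in pooled rate, and two with different behaviour can agree.

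The background also separates the hazards. A small-bowel tip that moves back to the stomach threatens absorption and tolerance, while a gastric tip that moves to the esophagus carries a still higher aspiration risk. The results are meant to inform how often placement is checked (section 3.1, item 2). A low pooled rate that comes mostly from small-bowel tubes would say little about gastric ones.

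The factor analysis (section 3.1, item 1) could be affected as well. A factor that happens to go with starting zone, such as length inserted, could appear related to migration because of where the tip began.

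**Working it through.** **Inputs from the documents:** 20 pilot patients, 62 assessments, 8 events, all in the small bowel.

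**Inputs assumed, because the documents do not give them:** the small-bowel share of assessments in the pilot (s) and in the new study (t), and the gastric migration rate (g).

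**1. Pilot pooled rate.** 8/62 = 12.9% per assessment. The exact binomial 95% interval is 5.7% to 23.9%. It ignores clustering, although patients contributed 62/20 = 3.1 assessments on average.

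**2. Effect of mix with g = 0.** The small-bowel rate is b = (8/62)/s, and the expected pooled rate in the new study is t × b.

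With s = 80%: b = 8/(0.80 × 62) = 16.1%.
- t = 50%: 0.50 × 16.1% = 8.1%
- t = 95%: 0.95 × 16.1% = 15.3%

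Both values lie inside 5.7% to 23.9%.

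**3. Wider assumptions, still with g = 0:**

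| Pilot share s | b | t = 20% | t = 50% | t = 80% | t = 100% |
|---|---|---|---|---|---|
| 80% | 16.1% | 3.2% | 8.1% | 12.9% | 16.1% |
| 50% | 25.8% | 5.2% | 12.9% | 20.6% | 25.8% |

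Only the corner values (3.2%, 5.2%, 25.8%) fall outside the pilot interval. With s = 80%, the new study's share would have to be below about 5.7/16.1, or roughly 36%, for mix alone to do this. Nothing in the documents indicates such a shift, and nothing rules it out.

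**4. If gastric tips do move (g > 0).** The pooled rate is g + t × (b − g), so moving t from 50% to 95% changes it by 0.45 × (b − g). At g = 0 and b = 16.1% this is 7.3 percentage points. It shrinks as g approaches b and vanishes when they are equal.

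**5. What the absence of gastric events in the pilot shows.** This depends on the missing denominator.
- With about 12 gastric assessments (20% of 62), zero events has a one-sided 95% upper bound of 1 − 0.05^(1/12) = 22%. Fisher's exact test of 0/12 against 8/50 gives p = 0.34.
- With 31 gastric assessments (50% of 62), the bound is 9%. Fisher's test of 0/31 against 8/31 gives p = 0.005.

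These tests also ignore clustering.

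**The case against.** The strongest reply is that the information is already there. Tip zone is an outcome item, direction of migration cannot be assigned without a prior position, the insertion tracing is required, and zone is read twice. The team could describe whether the new events again fall only in the small bowel. This stands. A reader might infer that the plan ignores zone or cannot show whether the pilot replicates, and the documents do not support that. They also never name 12.9% as the replication target. What remains is that no by-zone denominator, curve or comparison is specified. The general allowance for further analyses does not supply one, and a split chosen after seeing the data is weaker support for a replication claim.

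A second reply is that the illustration rests on assumed mixes and a zero gastric rate. This also stands. The zero rate sits badly with the background, which says that forward migration occurs and that clinicians rely on it to carry gastric tubes into the small bowel. A positive gastric rate below the small-bowel rate makes the effect of mix smaller.

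Third, two further inferences are tempting but unproven. The documents do not show that starting zone is the main determinant of migration: at the assumed 12 gastric assessments the pilot contrast is compatible with chance. Nor does any section link prokinetics or ileus to starting zone, so confounding of the factor comparison is possible, not demonstrated. Those factors are in any case exploratory, collected to help plan a larger study.

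**Conclusion.** The point holds in a limited form. Starting zone can be obtained from data the study already requires, yet it is neither an independent variable nor a stratum in any planned analysis. Because the pilot events were confined to the small bowel and the two tip positions carry different hazards, a pooled rate is a weak basis for judging replication and for any advice about gastric tubes.

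The size of the problem cannot be determined from the documents. The range of 8.1% to 15.3% rests on an assumed 80% pilot share, an assumed 50% to 95% share in the new study and an assumed zero gastric rate. A reader might take this near two-fold range as evidence that mix alone would produce an apparent failure to replicate. It does not show that, since the range lies within the pilot's own uncertainty.

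This is an inexpensive improvement that should be made. It does not invalidate the design.

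**What to change.** - Add two items to the independent variables in section 8.1: tip zone at insertion, from the required tracing, and tip zone at the start of each interval, from the previous tracing. Section 6.4 has a pulled-back tube advanced and the change noted on the form, but does not say that a new tracing follows. For those intervals, take the starting zone from the position noted and flag it as such.
- In section 8, report migration per interval and the recurrent-event curve separately for gastric and small-bowel starts, with the denominators for each.
- Make the comparison with the pilot by zone, giving the pilot's own denominators by zone.
- Include starting zone in the comparison of factors by migration status.
- State in advance that, if few tubes start in the stomach, conclusions are limited to small-bowel tubes.

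The cost is SAP wording plus a derived variable and a flag in the data set; no enrolment change is needed. The downside is wider intervals within each stratum, most of all in whichever zone has fewer tubes.

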3.1 Secondary Objectives

1. Identify factors associated such as mobility and position changes that may affect feeding tube migration.
2. Findings may inform recommendations for clinical practice regarding the frequency for FT placement verification.
3. Validate current dual verification process for feeding tube confirmation.

4. Study Population

The sample recruited for this study will include adult patients in critical care with small bore feeding tubes (FT) in acute and critical care. All participants must be able to understand and fluently speak English.

Investigators will review patient census and data from cortrak to identify new small bore feeding tube insertions in adult patients on the designated study units and will assess eligibility criteria. We are aiming for a sample of 120 feeding tubes.

Parkview Health, Fort Wayne, IN

- Surgical trauma ICU (STICU) and Medical ICU (MICU)

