4.2 Exclusion Criteria

- <18 years old
- Identified as “Doe”
- Unable to speak or understand English language
- Pregnancy
- Prisoners
- FT anticipated to be removed within 24 hours
- Contraindications to placing a mark on the abdomen for top foot of receiver unit (large dressings, open abdomen, halo vest, etc.)
- Original guidewire unavailable

5. Vulnerable Populations

No vulnerable populations will be targeted for enrollment but may be included except for pregnant patients and prisoners, which will be excluded.

6. Study Design

This study will use a longitudinal, repeated measures design replication study from previous pilot study.

An investigator will perform recruitment and data collection. Additional data collectors will be used as needed to ensure that data collection is performed daily, including weekends. Since this practice was safely completed in a pilot study as well as a previous study and is currently standard practice to assess tube location as needed, a waiver of written informed consent is being requested. Explanation will be provided to patients/family that we are evaluating the tube daily to assess any movement of the feeding tube.

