6.4 Methods: PI or Sub-I

- Investigators will discuss the study with the patient or designated family member so they understand the process steps.
- Label original Cortrak* guidewire with tape ("DrIFT Study") near orange Cortrak connector port.
- Obtain insertion tracings from original feeding tube insertion.

6.4.1 Subsequent Insertions:

- Verify that original guidewire is available (see tag on proximal end).
- Position patient supine, HOB elevated 30 degrees. If unable to place supine, document position
- Connect Cortrak to guidewire. Wipe guidewire with alcohol before insertion
- Position Cortrak receiver unit on abdomen. At the time of the first data collection, a surgical marker will be used to indicate location for placement of the top foot of the receiver unit (see image attached) on the patient's abdomen. Subsequent data collection will align the top foot of receiver unit with the mark on the patient's abdomen.
- Flush FT with 30ml water per institutional protocol.
- Insert guidewire into FT and obtain Cortrak insertion tracing to determine position of distal tip of feeding tube.
- Print 3 insertion tracings (anterior, lateral, depth/cross section). Write unique identifier on the back of each tracing printout. Do not write any other information on the insertion tracing.
- Remove guidewire, wipe with alcohol and leave in bag at the bedside.
- If tubes are found to be pulled back, this will be documented along with precipitating factors. Tube will then be advanced and will continue data collection noting the change in position on data collection form.

Other study data will be entered onto a hard copy, printed data collection form and stored temporarily in the locked office of the site Sub-II. Study data will be obtained from patient observation, discussion with the nurse, and the EMR.

7. Study Duration/ Study Timeline

The proposed study will take place over a 10 month period after IRB approval. Dissemination of study findings will take place via poster or podium presentation at an appropriate conference and also published in a peer-reviewed journal.

Study Timeline

	Dec	Jan 2024	Feb	March	April	May	June	July	Aug	Sept
IRB Submission										
Recruit Participants										
Perform /Data Collection										

DrIFT 2 STUDY: DISPLACEMENT IN FEEDING TUBES

Data Analysis										
Dissemination by poster/manuscript										

8. Statistical Analysis Plan

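### The bolus field asks for a volume but prints a rate unit (ml/hr), so one bolus regimen can be recorded as different numbers; a minor recording flaw in one exploratory variable

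*Combined protocol and SAP*

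**What the plan says.** Section 8.1 (Data Analysis) lists the independent variables. Under the bedside observations, one line covers continuous feeding, "Rate of formula ____ ml/hr", and the next covers bolus feeding, "Bolus via FT yes/no, volume ____ ml/hr, frequency: every ____ hours".

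The purpose of the list is given in the same section: "These variables that possibly have an association with FT migration will be collected and will help to inform the design of a larger R01 study". It serves the first secondary objective in Section 3.1: "Identify factors associated such as mobility and position changes that may affect feeding tube migration". Section 8 plans to compare characteristics by migration status, using "two-sample t-tests (or Wilcoxon for nonparametric) for continuous variables".

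On recording, Section 6.4 says "Other study data will be entered onto a hard copy, printed data collection form", and Section 6 adds "Additional data collectors will be used as needed to ensure that data collection is performed daily, including weekends". Section 10 has the forms completed by the principal investigator or a sub-investigator, with later entry into a spreadsheet. No section defines the bolus entry, gives a conversion rule or asks how long a bolus takes to run.

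**The concern.** The label and the unit on the bolus line contradict each other. A volume per bolus is in ml, and ml/hr is a rate. The separate interval makes sense only if the blank holds a volume, but the printed unit is the one used correctly on the continuous-feeding line just above. A recorder who follows the label and one who follows the unit will write different numbers for the same patient. The listed items would not show an analyst which was done.

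At stake is one continuous exploratory variable. If the entries mix conventions, a t-test or Wilcoxon test of bolus volume by migration status compares unlike quantities, and a summary of bolus volume passed to the later study would be unreliable. Enrolling more tubes would not cure mixed units.

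**Working it through.** The documents state no bolus volume, interval or duration, so there is no figure of theirs to reproduce. The check is one of dimensions, followed by an illustration whose numbers are all assumed.

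**1. Possible entries.** Let a bolus be V ml, given every H hours, delivered over D hours.

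| Reading of the blank | Entry | Recoverable from the listed fields? |
|---|---|---|
| Volume of one bolus (follows the label) | V | Yes |
| Average hourly volume (follows the unit) | V/H | Yes, multiply by H, if the convention is known |
| Rate while the bolus runs (follows the unit) | V/D | No, D is not collected |

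The ratio of the first to the second is V ÷ (V/H) = H. The ratio of the third to the second is (V/D) ÷ (V/H) = H/D. Neither depends on V.

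**2. Example (assumed: V = 240, H = 6, D = 0.5).**
- Entries: 240; 240/6 = 40; 240/0.5 = 480. Largest to smallest: 480/40 = 12, which equals H/D = 6/0.5.
- If an analyst read each entry as ml per bolus and derived a daily volume as entry × 24/H, the results would be 240 × 4 = 960, 40 × 4 = 160 and 480 × 4 = 1920 ml. The true value is 960 ml.
- Range: for H from 4 to 6 hours and D from 0.25 to 1 hour, H/D runs from 4/1 = 4 to 6/0.25 = 24. V and V/H alone differ 4- to 6-fold.

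**3. Effect of mixing (assumed regimens).** Take V equally likely to be 120, 180, 240, 300 or 360 ml, and H equally likely to be 4, 6 or 8 hours, independently. Then E(V) = 240, E(V²) = 64,800, Var(V) = 7,200, E(1/H) = 0.1806 and E(1/H²) = 0.0353. Write the entry as V × M, where M is 1, 1/H or 1/D according to the convention used. The correlation of the entry with the true per-bolus volume is

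E(M) × Var(V) ÷ √{Var(V) × [E(M²)E(V²) − E(M)²E(V)²]}.

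- All entries as V: 1.00.
- 20% as V/H: 6,020 ÷ √(7,200 × 12,030) = 0.65.
- 50% as V/H: 4,250 ÷ √(7,200 × 13,474) = 0.43.
- Equal thirds of V, V/H and V/D with D = 0.5: 0.43.

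One caution on step 3. In this assumed mix V/H never exceeds 360/4 = 90, while V is at least 120, so an analyst could separate those two conventions by size. Entries of V (120 to 360) and V/D (240 to 720) overlap and could not be separated that way. Smaller boluses would also make V overlap with V/H.

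**4. What does not depend on this field.** The outcome is migration and tip zone read from the tracings. The Kaplan-Meier analysis uses time to migration. The sample-size statement, "A sample size of 120 will detect feeding tube migration over time (effect size 0.18, 80% power, alpha 0.05) using mixed effects model", does not involve bolus volume. The bolus yes/no item and the interval are unambiguous.

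**The case against.** The case against is that this is a unit slip with an obvious intended meaning. The label and the interval both point to volume per bolus, and the continuous rate has its own line. Section 10 names the principal investigator and sub-investigators as form-fillers, and Section 6 allows extra collectors only as needed. A small team could share one unwritten convention, and the values would then be analysable. The list in Section 8.1 is not the form itself. The printed form is not in the documents and may carry instructions. The first secondary objective names mobility and position as its examples, not feeding, and no test names bolus volume.

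Most of this stands, and it limits the point. A reader might infer that entries will mix, or that bolus volume cannot be analysed reliably. The documents show only that entries can mix. A reader might also take the 12-fold spread as an expected error, but it is simply H/D for assumed values and says nothing about how often the blank would be misread. Nor is bolus volume shown to be unusable on a common scale with the continuous rate, because the plan proposes no such scale.

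The contradiction itself is not answered. The line as written gives a unit that does not fit its label, more than one recorder is possible, and no section settles the meaning.

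**Conclusion.** The bolus line is internally inconsistent and should be corrected. The consequence is possible blurring of one exploratory variable among many, and of what that variable can contribute to the later study. Severity is minor.

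That the same regimen can be recorded as V or V/H, differing by a factor of H, follows from the line itself and needs no assumption. How much harm results depends on three things the documents do not give: how many patients receive boluses, how recorders read the blank, and whether the printed form gives an instruction. If few patients are bolus-fed, or all recorders use one convention, the practical effect is close to nil. It would be wrong to infer any threat to the migration finding or to the power claim, since neither uses this field.

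**What to change.** Reword the bolus line in Section 8.1 and on the printed form as: bolus via FT, yes/no; volume ____ ml per bolus; every ____ hours. Keep ml/hr for the continuous-formula line only. If a daily figure is wanted, derive it as volume × 24/interval. Add a delivery-time item only if a delivery rate is of interest.

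For forms already completed with the present unit, check the entry against the EMR where it records bolus volume. Section 6.4 names the EMR as a general source, but Section 8.1 places this item under bedside observation, so recovery is not assured. Where the value cannot be confirmed, analyse only bolus yes/no and interval for that record, and report how many records this affects.

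The cost is one unit on the form, plus a look-back limited to any bolus-fed patients already enrolled. It changes recording only, not feeding, and leaves the sample size and planned tests as they are.
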